## **Protocol synopsis**

**Title of study:** A six month, single-center, feasibility study of the use of the Intuitive Surgical da Vinci® Single-Site™ Instruments and Accessories for Single-Port Laparoscopic Nephrectomies

**Purpose and rationale:** After being informed of the potential risks and off-label use of the da Vinci Single-Site approach in our study, patients will undergo a robotic-assisted single-site donor nephrectomy performed by a two-surgeon team utilizing existing da Vinci instrumentation and Single-Site platforms. Renal mobilization and vascular dissection will be performed with manual laparoscopy performed for vascular division utilizing stapling devices.

**Objectives:** The primary objective is to measure the feasibility of the current Single-Site platform to perform donor nephrectomy prior to vascular division and kidney extraction.

[figure not shown]
**Population:** The proposed study population consists of adults aged between 18-70 who have been previously approved by the living donor transplant committee at the University of Maryland Medical Center as appropriate candidates for renal donation.

**Inclusion criteria:** The following criteria must be met in order for a patient to participate in the study. Male or female adults ages from 18 to 70 who are good general health, and who have a genuine altruistic motivation. The patient must also have compatible blood type with the recipient, a body mass index less than 35, and appropriate for left kidney donation. Approval by the Living Donor Center must also be met in order to participate in the trial.

**Exclusion criteria:** The following criteria will exclude any patients from participating in the clinical trial. Any patients suffering from cancer, diabetes, kidney disease, heart disease, liver disease, sickle cell disease, HIV or hepatitis, previous major abdominal surgery, or more than two left renal arteries.

**Study design:** After obtaining informed consent patients will be screened for eligibility. Patients will undergo a robotic-assisted single-incision laparoscopic donor nephrectomy with the use of the da Vinci Surgical System with the Single-Site platform.

Figure 1-1 Study Design

**Efficacy assessments:** Measurement of the ability of the current Single-Site platform to assist laparoscopic donor nephrectomy procedure prior to final extraction of the donor kidney.

**Data analysis:** Statistical analysis will be performed on ergonomic and other collected data during the operative procedures and compared to matched patients. The proposed study of 20 patients may not generate statistically significant conclusions; however, we believe our observations will provide valid conclusions that support the use and continued development of robotic single port donor nephrectomy.

**Sample size justification:** The sample size was determined to provide a pilot group that could potentially demonstrate the efficacy of the da Vinci Surgical System with the Single-Site platform in donor nephrectomies.

## **1.0 Background**

Minimally invasive surgery has been an important factor responsible for the expansion of living renal donation since its advent over a decade ago. Presently, more than 6000 laparoscopic donor nephrectomies are performed annually in the United States. While the number of living kidney donors has plateaued over the last decade, the number of recipients awaiting transplantation has more than doubled to nearly 90,000. Refinements in minimally invasive surgical approaches may encourage additional suitable individuals to consider kidney donation.

Laparoendoscopic single site (LESS) surgery was introduced as one technique to further decrease the invasiveness of laparoscopic surgical approaches. We initiated our single-port donor nephrectomy program in 2009 and have reported the World's largest series. This series clearly supports the safety and improved outcomes associated with this approach. New instrumentation may further decrease the learning curve and operative times associated with single-port techniques. The robotic single-port platform has demonstrated feasibility in a variety of procedures.

Our center has performed over 200 single-port donor nephrectomies with standard laparoscopy and has reported patient benefits associated with a single port approach. The single port robotic platform offers the potential to ameliorate the significant technical and ergonomic challenges that currently limit more widespread application of single port donor surgery.

## **2.0 Purpose and rationale**

After being informed of the potential risks and off-label use of the da Vinci Single-Site approach in our study, patients will undergo a robotic-assisted single-site donor nephrectomy performed by a two-surgeon team utilizing existing da Vinci instrumentation and Single-Site platforms. Renal mobilization and vascular dissection will be performed with manual laparoscopy performed for vascular division utilizing stapling devices.

## **3.0 Objectives**

### **3.1 Primary objective**

The primary objective is to measure the feasibility of the current Single-Site platform to perform donor nephrectomy prior to vascular division and kidney extraction.

### **3.2 Secondary objectives**

Secondary objectives include operative times, blood loss, and surgeon ergonomics as measured via techniques developed in our surgical simulation center.

## **4.0 Study design**

[figure not shown]
**Hypothesis:** We believe that the da Vinci system and its single port platform will offer solutions to the challenges of visualization, instrument articulation, and ergonomics that limit the widespread application of single-port donor nephrectomy as the preferred approach for renal donation.

**Methods:** We will perform an IRB-approved study of the use of the da Vinci Surgical System with Single-Site technology in donor nephrectomies. The IRB proposal and consent will be constructed to provide kidney donors with the opportunity to participate in our study. Patients will be informed of the potential risks and off-label use of the da Vinci Single-Site approach in our study. Because the standardized approach for renal donation at our center is single port donor nephrectomy, we anticipate enrollment of up to 20 patients for this study.

Patients will undergo robotic-assisted single-site nephrectomy performed by a two-surgeon team utilizing existing da Vinci instrumentation and Single Site platforms. Renal mobilization and vascular dissection will be performed with conversion to standardized laparoscopy for the final stages of vascular division with stapling devices and extraction. The primary objective is a feasibility measure of the ability of the current Single-Site platform to perform major portions of the procedure. Secondary objectives include operative times, blood loss, and surgeon ergonomics as measured via techniques developed in our surgical simulation center. Study cases will be compared to existing matched cohorts of single port donor nephrectomy cases performed by manual laparoscopy. The study population will include adults aged 18 to 70 of both genders who meet our center's criteria for renal donation and who consent to participate in the study. Our sample size of 20 patients is proposed to initiate this pilot study of the feasibility of robotic single port donor nephrectomy.

Statistical analysis will be performed on ergonomic and other collected data during the operative procedures and compared to matched patients. The proposed study of 20 patients may not generate statistically significant conclusions; however, we believe our observations will provide valid conclusions that support the use and continued development of robotic single port donor nephrectomy techniques.

Table 1 Study Design

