### **7.3 Efficacy**

The observations to assess efficacy of the investigational device include the proportion of the surgical procedure able to be performed with the device, prior to standard laparoscopic techniques that will be employed in the final surgical steps. Efficacy will be specifically measured in operative time, blood loss, and successful completion of donation. Post-operative assessments will include patient satisfaction and recovery surveys. The efficacy variables selected are standard for this indication/patient population.

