## **10.3 Analysis of the primary objective(s)**

### **10.3.1 Variable**

The primary objective is a feasibility assessment of the ability of the current Single-Site platform to perform major portions of the procedure prior to vascular division and extraction. This is a feasibility clinical study design to collect the primary evidence of safety and efficacy to support a marketing submission or application.

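### The primary feasibility objective has no stated analysis and no criterion fixed in advance for feasible or not feasible, while the protocol already expects a supportive conclusion

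*Combined protocol and SAP*

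**What the plan says.** Section 3.1 sets the aim: "The primary objective is to measure the feasibility of the current Single-Site platform to perform donor nephrectomy prior to vascular division and kidney extraction". Section 10.3.1 restates it as a "feasibility assessment of the ability of the current Single-Site platform to perform major portions of the procedure prior to vascular division and extraction". Section 4.0 names the steps to be done on the platform (mobilizing the kidney and dissecting the vessels) and the planned switch to standard laparoscopy for dividing the vessels and extraction.

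The nearest thing to a measurement is in 7.3, where the observations include "the proportion of the surgical procedure able to be performed with the device". The same section adds: "Efficacy will be specifically measured in operative time, blood loss, and successful completion of donation". None of these has a required level.

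Section 10.3 has a single subsection, on the variable, and describes no analysis. Section 10.1 makes all analyses descriptive and rules out tests, 10.5 gives 20 patients with no calculation, and 10.7 (interim analysis) gives only follow-up times.

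On the expected outcome, 4.0 says "we believe our observations will provide valid conclusions that support the use and continued development of robotic single port donor nephrectomy techniques", after conceding that 20 patients may not give statistical significance. The synopsis has the same sentence, one word shorter. Section 10.3.1 adds that the study is to supply the main safety and efficacy evidence for a marketing application.

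**The concern.** A feasibility study should say beforehand what result would lead it to conclude that the procedure is not feasible as configured. Here the bar is performance of the major parts of the operation, with no per-patient definition and no count. It would therefore be set after the results are known, by investigators who have already recorded that they expect the observations to be supportive.

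The participants are healthy living donors, the device use is off-label, and the results are meant for a marketing application. If half or three quarters of the cases reach the planned switch point on the platform, the report could call this feasible or not feasible with equal support from the plan.

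**Working it through.** **1. Is there a figure to reproduce?** No. The sample size of 20 (10.5) comes with no target rate, unacceptable rate, error rate or power, so no formula leads to it.

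**2. Where could a criterion sit?**

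| Place | What it gives | What it lacks for the primary objective |
|---|---|---|
| 3.1, 10.3.1 | Feasibility up to division of the vessels | Per-patient success, cut-off, analysis |
| 4.0 | Robotic steps and switch point; one-directional hypothesis | Required count; handling of unplanned early conversion |
| 7.3 | Share of the procedure done with the device; time, blood loss, completion | Unit for the share; acceptable level for any measure |
| 7.4 | Safety compared with the center's own rates | The rates; a consequence; bearing on feasibility |
| 10.4.1 | Secondary measures compared with matched manual cases | Margin; consequence |
| 10.1, 10.5 | Descriptive analysis; 20 patients | Target |

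No entry links a result on the primary objective to a conclusion. Under the plan, 10 of 20 and 20 of 20 lead to the same specified action, which is to describe them.

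**3. How wide is the ambiguous middle?** Suppose each patient is scored as success or failure. The exact (Clopper-Pearson) 95% limits for x successes out of n = 20 are the 0.025 quantile of Beta(x, n − x + 1) and the 0.975 quantile of Beta(x + 1, n − x).

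| Successes | Observed | Exact 95% CI |
|---|---|---|
| 0 of 20 | 0% | 0% to 17% |
| 10 of 20 | 50% | 27% to 73% |
| 12 of 20 | 60% | 36% to 81% |
| 15 of 20 | 75% | 51% to 91% |
| 16 of 20 | 80% | 56% to 94% |
| 20 of 20 | 100% | 83% to 100% |

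The extremes speak for themselves. The intervals for 10 and 15 successes overlap from 51% to 73%, and the plan labels neither.

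**4. Can 20 patients support a rule?** The documents give no rates, so the cut-offs and true rates here are assumptions for illustration: feasible at 16 or more, indeterminate at 13 to 15, not feasible at 12 or fewer. With X distributed as Binomial(20, p), the three probabilities are P(X ≥ 16), P(13 ≤ X ≤ 15) and P(X ≤ 12).

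| True rate p | Feasible | Indeterminate | Not feasible |
|---|---|---|---|
| 50% | 1% | 13% | 87% |
| 60% | 5% | 36% | 58% |
| 70% | 24% | 53% | 23% |
| 80% | 63% | 34% | 3% |
| 90% | 96% | 4% | 0.04% |

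So the rule separates 60% from 90% well. It does not separate 70% from 80%.

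**5. Other cut-offs.** A bar of 17 passes a true 60% with probability 0.016 and a true 90% with 0.867. A bar of 18 passes a true 70% with probability 0.036, but a true 90% with only 0.677. Good discrimination needs rates about 25 points or more apart.

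**6. Fewer than 20 operated.** Section 4.0 says up to 20. Keeping the 80% bar at n = 10 means 8 of 10, and P(X ≥ 8 | n = 10, p = 0.6) = 0.167, against 0.051 for 16 of 20. A fixed percentage does not keep the rule's properties.

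**The case against.** The strongest reply is that this is an openly unpowered, descriptive, single-center pilot. Such a study may estimate a proportion and leave the judgement to its readers. That is fair as far as power and testing go, and neither is asked for. It is weaker on the missing criterion, because 10.3.1 intends the results for a marketing application and a count fixed in advance fits a descriptive plan.

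A reader might infer that the supportive conclusion is already fixed and that no result could be negative. The documents do not support that. The sentence states a belief, the analysis section commits to no conclusion, and 0 of 20 or 5 of 20 would be plainly unfavourable. Nor do they say that half the cases being converted early would be written up as support; that would be a prediction about the sponsor.

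It is also tempting to say that the target is empty. It is not: 4.0 names the steps and the switch point, and 7.3 names an observation. The comparisons in 7.4 and 10.4.1 can come out unfavourably too. Tests are not wholly excluded, since the synopsis and 4.0 announce statistical analysis and 10.4.2 allows exploratory tests. But none of these carries a value, margin or consequence for the primary objective.

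Finally, the 16 and 12 cut-offs have no source in the documents. That stands, so they serve only as an illustration.

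**Conclusion.** The point holds in this form: the primary objective has no stated analysis and no prespecified feasibility criterion, and the anticipatory sentence in the synopsis and 4.0 has nothing beside it that could contradict it. The practical effect is confined to intermediate results, roughly 10 to 15 of 20, where the reading would be chosen after the data are seen. It should be corrected, but it does not stop the study from being run.

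The absence of a criterion is read from the available text, whose numbering passes from section 7 to section 10 and whose figures are not shown. The probabilities assume independent patients with a common success rate. With so few surgeons and a possible learning effect, that is a simplification. The illustrative bar of 16 separates only widely spaced rates.

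**What to change.** - **Synopsis and 4.0:** replace the expectation of support with neutral wording, for example that the observations will be used to judge whether the technique warrants further development.
- **10.3.1, definition:** a patient is a success if the steps named in 4.0, renal mobilization and vascular dissection, are completed on the platform up to the planned switch for vascular division. An unplanned earlier conversion counts as a failure. This is a scoring rule for analysis and does not bear on when a surgeon should convert.
- **10.3.1, criterion:** before the first case, fix the counts out of 20 to be read as feasible, indeterminate and not feasible. The investigators choose them; 16 or more, 13 to 15, and 12 or fewer are an illustration only. State the operating characteristics of the chosen rule.
- **Reporting:** give the count with its exact 95% CI, as a descriptive criterion and not a test.
- **Fewer than 20 operated:** report the proportion and CI, and recompute the operating characteristics for the actual number. Do not carry over the percentages.

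The cost is protocol wording. No patients are added, and the data come from the operative record. The sponsor commits to a bar and may have to report that it was missed. With 20 patients the illustrative rule will often be inconclusive when the true rate is near 70% to 80%.

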## 5.0 Population

The proposed study population consists of adults aged between 18-70 who have been previously approved by the living donor transplant committee at the University of Maryland Medical Center as appropriate candidates for renal donation.

### 5.1 Inclusion criteria

The following criteria must be met in order for a patient to participate in the study. Male or female adults ages from 18 to 70 who are good general health, and who have a genuine altruistic motivation. The patient must also have compatible blood type with the recipient, a body mass index less than 35, and appropriate for left kidney donation. Approval by the Living Donor Center must also be met in order to participate in the trial.

## **5.2 Exclusion criteria**

The following criteria will exclude any patients from participating in the clinical trial. Any patients suffering from cancer, diabetes, kidney disease, heart disease, liver disease, sickle cell disease, HIV or hepatitis, previous major abdominal surgery, or more than two left renal arteries.

## **6.0 Treatments**

The study is a feasibility study. Patients will undergo a donor nephrectomy with the assistance of the investigational device, the da Vinci Surgical System with the Single-Site Instruments and Accessories.

### **6.1 Investigational device**

The investigational device, the da Vinci Surgical System with the Single-Site Instruments and Accessories will be used to perform major portions of the procedure prior to vascular division and extraction.

### **6.2 Treatment arms**

During pre-admission testing, if the patient has met all inclusion/exclusion criteria, patients will be enrolled into the treatment group.

### **6.3 Treatment assignment**

Once a potential study patient is identified and he/she fulfills the inclusion/exclusion criteria and the informed consent form is signed, the patient will be entered into the study. The patient will be assigned a patient identification number (see Section 6.5.1).

### **6.4 Treatment blinding**

Not applicable

### **6.5 Treating the patient**

#### **6.5.1 Patient numbering**

Each patient is uniquely identified in the study by a patient number. The first patient is assigned patient number 1, and subsequent patients are assigned consecutive numbers (e.g. the second patient is assigned patient number 2, the third patient is assigned patient number 3). Once assigned to a patient, a patient number will not be reused. If the patient fails to be enrolled for any reason, the reason for not being enrolled will be entered on the Screen Failure eCRF.

#### **6.5.2 Use of the study device**

The study site will be supplied with an investigational device by Intuitive Surgical Systems and it will be used by three qualified surgeons.

**6.5.3 Study device supply, storage and tracking**

The study device will be received by a designated person at the study site, handled and stored safely and properly, and kept in a secured location to which only the investigator and designated assistants have access. Upon receipt, all study devices will be stored according to the instructions specified on the device labels. Clinical supplies will be dispensed only in accordance with the protocol. Device labels will be in the local language and comply with all legal requirements. The investigator will maintain an accurate record of the shipment and dispensing of study device in a device accountability ledger. Monitoring of device accountability will be performed by the field monitor during site visits and at the completion of the trial. All unused study devices, packaging, and device labels will be destroyed in conformance to University of Maryland Medical Center policies.

**6.5.4 Instructions using study device** Not applicable.

**6.5.5 Permitted study device adjustments and interruptions** Not applicable.

**6.5.6 Study device discontinuation and premature patient withdrawal** Not applicable.

**6.5.7 Emergency unblinding of treatment assignment** Not applicable.

**6.5.8 Study completion and post-study treatment**

At study completion CRF page should be completed after the operation. Due to the nature of the study (a onetime exposure to the investigational device during the surgical procedure) withdrawal from the study cannot occur. Subjects who wish to withdraw from the study follow up will be permitted to do so.

**7.0 Visit schedule and assessments**

Table 7-1 lists all of the assessments and indicates with an “x” the visits when they are performed.

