**Table 1 Assessment schedule**

	Baseline	Week		
--	----------	------	--	--

Time Point	0	2	4	26
Visit Number	1	3	4	5
Informed Consent	X			
Background Information	X			
Inclusion/Exclusion	X			
Med Hist/Demography	X			
Vital Signs	X	X	X	X
Physical Exam	X	X	X	X
Laboratory Tests	X	X	X	X

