### **10.4.2 Safety**

Safety variables to be assessed include discontinuation from study, discontinuation from treatment, renal function, AE/infection, SAE, notable events, laboratory tests, and vital signs.

Adverse events will be summarized by presenting, for each treatment group, the number and percentage of patients having any adverse event, having an adverse event in each organ system and having each individual adverse event. The same type of summaries will be provided for serious adverse events and for events suspected to be related to the study device. Any other information collected (e.g. severity or relatedness to study device) will be listed as appropriate.

Laboratory data will be summarized by baseline values to most extreme post-baseline values, by presenting summary statistics of raw data and change from baseline values (means, medians, standard deviations, ranges) and by the flagging of notable values in data listings.

Data from other tests (e.g. vital signs) will be listed, notable values will be flagged, and any other information collected will be listed as appropriate. Any statistical tests performed to explore the data will be used only to highlight any interesting comparisons that may warrant further consideration.

The data collected will be presented in listings, summary tables and graphs.

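### The assessment table skips visit 2 and schedules no laboratory test or vital sign between the operation and about day 14, although the device is used once, at surgery

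*Combined protocol and SAP*

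**What the plan says.** Section 7.0 introduces the schedule: "Table 7-1 lists all of the assessments", with a mark at each visit where an assessment is done. The table that follows is headed Table 1, not 7-1. Its time-point row reads "Time Point 0 2 4 26" (weeks) and its visit row reads "Visit Number 1 3 4 5". Three rows are marked at every visit: physical exam, "Vital Signs X X X X" and "Laboratory Tests X X X X".

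Section 6.5.8 describes the exposure as "a onetime exposure to the investigational device during the surgical procedure".

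Section 10.4.2 states: "Safety variables to be assessed include discontinuation from study, discontinuation from treatment, renal function, AE/infection, SAE, notable events, laboratory tests, and vital signs". It then summarises laboratory data from baseline to the most extreme value after baseline, with change from baseline, and lists vital signs with notable values flagged.

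Other perioperative data are named outside the table. Sections 7.3 and 7.4 cover operative time, blood loss, intraoperative complications or injuries, and completion of donation. Section 7.5.1 covers hospitalizations, with reason for admission and length of stay. Section 10.4.2 tabulates adverse and serious adverse events. Section 10.7 places routine follow-up at 2 weeks and 6 months after the operation.

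**The concern.** With a single exposure at surgery, the days most informative about acute harm are the operation and early recovery. The schedule leaves that interval without any laboratory or vital-sign occasion, and the skipped visit number suggests that a perioperative visit was intended but not written in.

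The effect falls on the 10.4.2 laboratory summary. A worst-value summary depends on when values are sampled. If the first post-operative value comes at about two weeks, the worst recorded value may reflect recovery and not the acute effect of surgery. A fall in haemoglobin or a rise in creatinine that had resolved by then would leave no trace in that summary, which could look more favourable than the in-hospital course. Participants are donors required to be in good general health, and section 10.3.1 says the study collects primary evidence of safety and efficacy for a marketing submission, so the completeness of the early safety record matters.

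**Working it through.** The plan gives no calculated figure on this point. The check is a reading of the schedule against every other section that gives a collection time.

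**Where week 0 falls.** The week 0 column carries informed consent, eligibility and history. Section 6.2 enrols patients at pre-admission testing, and section 7.2 collects baseline data once consent and eligibility are settled. Week 0 is therefore before the operation.

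**Where the next visit falls.** Table 1 gives week 2. Section 10.7 counts 2 weeks from the operation. Taking the operation as day 0:

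| Visit | Week | Approximate day (week × 7) | Laboratory tests and vital signs |
|---|---|---|---|
| 1 | 0 | before the operation | marked |
| 2 | not in table | – | – |
| 3 | 2 | 2 × 7 = 14 | marked |
| 4 | 4 | 4 × 7 = 28 | marked |
| 5 | 26 | 26 × 7 = 182 | marked |

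**Count.** There are 4 scheduled occasions: 1 before the operation and 4 − 1 = 3 after it. Of those 3, the number on days 0 to 13 is 0. If the week 4 visit is dropped to match section 10.7, 2 post-operative occasions remain, and the number on days 0 to 13 is still 0.

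**Consequence for 10.4.2.** If only scheduled values are recorded, the most extreme post-baseline value for a patient is the worst of at most 3 readings, the earliest at about day 14.

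**Do other sections fill the interval?**

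- Section 7.4 gives blood loss, complications and injuries, but no laboratory value or vital sign.
- Section 7.5.1 gives admission reason and length of stay, but no laboratory value or vital sign.
- Section 6.5.8 calls for a CRF page after the operation but does not give its contents.
- Section 10.4.2 names the safety variables but gives no collection times.

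No section schedules an inpatient laboratory test or vital sign.

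**The case against.** Four points on the other side carry weight.

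**The table is not exhaustive, whatever section 7.0 says.** SF-36, blood loss, operative time, ergonomics, hospitalization data and adverse events are all planned and none has a row. It works as a clinic-visit schedule, so absence from it does not prove that something will not be collected. This stands, and the missing rows are a defect in their own right. The difference is that those items are named elsewhere as data to be collected, whereas inpatient laboratory tests and vital signs are scheduled nowhere.

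**Early harm has other routes into the data.** A reader might infer that any early harm is missed in all patients. The documents do not support that. Blood loss and intraoperative injury are recorded directly, hospital stays are recorded, adverse and serious adverse events are tabulated with no start at week 2, and 10.4.2 does not limit its worst-value summary to scheduled visits. A bleed or renal injury that needed treatment could well appear. These routes are incomplete, however. Section 7.5.2 sends the recording of adverse events to instructions in section 7.5.1, which concerns resource utilization and contains none. Event counts also do not supply the change from baseline that 10.4.2 promises.

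**A column may have been lost.** A jump from visit 1 to visit 3 is what a dropped perioperative column would leave when a PDF is converted to text. This cannot be excluded. Against it, the time-point row, the visit row and all three fully marked rows have four cells each, and section 10.7 fits a first follow-up at 2 weeks.

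**Laboratory tests and vital signs are not a stated objective.** A reader might take the gap as a failure of a safety objective. Sections 3.1 and 3.2 list feasibility, operative times, blood loss and ergonomics. Laboratory tests and vital signs are safety variables in 10.4.2, and the measures that section 7.4 compares with centre rates do not depend on the missing visit.

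**Conclusion.** The concern holds in limited form. As written, 0 of 3 post-baseline laboratory and vital-sign occasions fall between the operation and about day 14, in a study of up to 20 patients exposed once, at surgery. The laboratory summary in 10.4.2 would then miss a transient change that resolves by week 2, unless unscheduled inpatient values are recorded. The primary feasibility objective is unaffected, and so are blood loss and intraoperative complications.

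The conclusion assumes that:

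- the table in the source PDF has no visit 2 column;
- week 2 is counted from the operation, as section 10.7 indicates;
- the laboratory row at follow-up includes the haematology (with haemoglobin) and serum creatinine that section 7.2 lists at baseline.

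How often such transient changes would occur cannot be estimated from the documents. The point deserves correction because the early interval matters most for a single exposure and the correction is cheap.

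**What to change.** 1. Check the source PDF for a visit 2 column. If one is there, the scheduling gap closes to the extent that its marks cover these rows.
2. If not, add an operation-to-discharge visit to the table. Add rows for the assessments named only in the text (blood loss, operative time, ergonomics, complications, adverse events, hospitalization, SF-36), and make the table number agree with section 7.0.
3. State that dated vital signs, haematology and serum creatinine are transcribed to the CRF for every patient wherever the hospital record contains them. That they are routinely available is an assumption; the documents do not say so. The proposal asks for no new test and no change in care. Setting the rule beforehand keeps extraction uniform across patients.
4. In 10.4.2, include these values as an in-hospital period shown separately from the later visits, and report how many patients contribute values.
5. Reconcile the week 4 visit in the table with section 10.7, which lists only 2 weeks and 6 months, and correct the cross-reference in section 7.5.2 for recording adverse events.

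The cost is one table column, the added rows, and a CRF page filled from the hospital record for up to 20 patients. The downside is extra data entry and safety tables that may look less favourable.
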